12.1.4 Safety Analyses

Table 89: Overall Summary of Adverse Events

	Placebo	Oxytocin	Total	
	(N=xx)	(N=xx)	(N=xxx)	p-value ¹
Number of AEs	XX	XX	XX	
Number of SAEs	XX	XX	XX	
Number (%) of subjects with at least one AE	xx (xx.x%)	xx (xx.x%)	xx (xx.x%)	0.xxx
Number (%) of subjects with at least one SAE	xx (xx.x%)	xx (xx.x%)	xx (xx.x%)	0.xxx
Number (%) of subjects with at least one AE related ² to study product	xx (xx.x%)	xx (xx.x%)	xx (xx.x%)	0.xxx
Number of AEs by severity				
Mild	XX	XX	XX	
Moderate	XX	XX	XX	
Severe	XX	XX	XX	
Life-threatening	XX	XX	XX	
Number of AEs by relationship to study product				
At least possibly related	XX	XX	XX	
Unrelated	XX	XX	XX	
Number of AEs by SAE status				
No	XX	XX	XX	
Yes	XX	XX	XX	

¹p-value from chi-square test ² Related is possible, probable, or definite

Table 90: Number and Percentage of Subjects with Adverse Events

MedDRA System Organ Class/	Placebo	Oxytocin	p-value ¹
Preferred Term	(N=xx)	(N=xx)	
- Any Adverse Events -	xx (xx.x%)	xx (xx.x%)	0.xxx
SOC			
- Overall -	xx (xx.x%)	xx (xx.x%)	0.xxx
Preferred term 1	xx (xx.x%)	xx (xx.x%)	
Preferred term 2	xx (xx.x%)	xx (xx.x%)	

Multiple occurrences of a specific adverse event for a subject are counted once in the frequency for the adverse event. Likewise, multiple occurrences of adverse events within a specific preferred term for a subject are counted once in the frequency for the preferred term.

Programmer's Notes: Order System Organ Class alphabetically and preferred term alphabetically within System Organ Class.

¹ Fisher's exact test

Table 91: Number and Percentage of Subjects with Adverse Events During Weeks 1 & 2

Same as Table 90 except only the first 2 weeks

Table 92: Number and Percentage of Subjects with Adverse Events During Weeks 3-12

Same as Table 90 except only the last 10 weeks

Table 93: Summary of Subjects with Adverse Events by Severity and Relationship – Oxytocin

	Number of Subjects (%) (N=x)													
		M	ild	Mod	lerate	Sev	vere	Life-thr	eatening		All Grades			
	MedDRA	R	NR	R	NR	R	NR	R	NR	R	NR	R + NR		
SOC	PT													
		XX	XX	XX	XX	XX								
		(xx.x%)	(xx.x%)	(xx.x%)	(xx.x%)	(xx.x%)								

Notes: Events are counted once per subject at the highest severity grade and closest relationship to the investigational product. R= related to investigational product (possibly, probably, definitely). NR = not related to investigational product (unrelated, unlikely).

Table 94: Summary of Subjects with Adverse Events by Severity and Relationship – Placebo

	Number of Subjects (%) (N=x)													
	Mild Moderate Severe Life-threatening All Grades													
SOC	MedDRA PT	R	NR	R + NR										
		xx (xx.x%)												

Notes: Events are counted once per subject at the highest severity grade and closest relationship to the investigational product. R= related to investigational product (possibly, probably, definitely). NR = not related to investigational product (unrelated, unlikely).

Table 95: Number and Percentage of Subjects with Adverse Events by Maximum Severity

MedDRA SOC/		Pla	cebo		Oxytocin			
Preferred Term		(N=xx)				(N=	=xx)	Т
	Mild	Moderate	Severe	Life- threatening	Mild	Moderate	Severe	Life- threatening
- Any Adverse Events - SOC	nn (xx.x%)							
- Overall - Preferred term 1	nn (xx.x%) nn (xx.x%)							
Preferred term 2	nn (xx.x%)							

Multiple occurrences of a specific adverse event for a subject are counted once in the frequency for the adverse event. Likewise, multiple occurrences of adverse events within a specific preferred term for a subject are counted once in the frequency for the preferred term.

Programmer's Notes: Order System Organ Class alphabetically and preferred term alphabetically within System Organ Class.

Table 96: Number and Percentage of Subjects with Adverse Events by Maximum Severity During Weeks 1& 2

Same as Table 95 using only first 2 weeks

Table 97: Number and Percentage of Subjects with Adverse Events by Maximum Severity During Weeks 3-12

Same as Table 95 using only weeks 3-12

Table 98: Number and Percentage of Subjects with Adverse Events Occurring in >= 5%

MedDRA SOC/	Placebo	Oxytocin	
Preferred Term	(N=xx)	(N=xx)	p-value ¹
SOC	nn (xx.x%)	nn (xx.x%)	0.xxx
- Overall -			
Preferred term 1	nn (xx.x%)	nn (xx.x%)	0.xxx
Preferred term 2	nn (xx.x%)	nn (xx.x%)	0.xxx

Multiple occurrences of a specific adverse event for a subject are counted once in the frequency for the adverse event. Likewise, multiple occurrences of adverse events within a specific preferred term for a subject are counted once in the frequency for the preferred term. At least 5% occurring in either arm to be included in the table.

1 Fisher's Exact test

Programmer's Notes: Order System Organ Class alphabetically and preferred term alphabetically within System Organ Class.

Table 99: Number and Percentage of Subjects with Adverse Events Leading to Discontinuation of Study

MedDRA SOC/	Placebo	Oxytocin
Preferred Term	(N=xx)	(N=xx)
		I
SOC	nn (xx.x%)	nn (xx.x%)
- Overall -		
Preferred term 1	nn (xx.x%)	nn (xx.x%)
Preferred term 2	nn (xx.x%)	nn (xx.x%)
	nn (xx.x%)	nn (xx.x%)

Notes: Percentages are based on the total number of subjects, as given in the column heading.

Multiple occurrences of a specific adverse event for a subject are counted once in the frequency for the adverse event. Likewise, multiple occurrences of adverse events within a specific preferred term for a subject are counted once in the frequency for the preferred term.

Programmer's Notes: Order System Organ Class alphabetically and preferred term alphabetically within System Organ Class.

Table 100: Number and Percentage of Subjects with Adverse Events Leading to Discontinuation of Study Medication

MedDRA SOC/	Placebo	Oxytocin
Preferred Term	(N=xx)	(N=xx)
SOC	nn (xx.x%)	nn (xx.x%)
- Overall -		, , ,
Preferred term 1	nn (xx.x%)	nn (xx.x%)
Preferred term 2	nn (xx.x%)	nn (xx.x%)
	nn (xx.x%)	nn (xx.x%)

Multiple occurrences of a specific adverse event for a subject are counted once in the frequency for the adverse event. Likewise, multiple occurrences of adverse events within a specific preferred term for a subject are counted once in the frequency for the preferred term.

Programmer's Notes: Order System Organ Class alphabetically and preferred term alphabetically within System Organ Class.

Table 101: CIWA-AR Score ≥ 10 at Least Once During Treatment

							95%	CI
	Placebo	Oxytocin	Total					
	(N=xx)	(N=xx)	(N=xxx)	p-value ¹	Cohen's h	Odds Ratio	OR Lower CI	OR Upper CI
CIWA-AR Score >= 10								
Never	xx (xx.x%)	xx (xx.x%)	xx (xx.x%)					
At Least Once	xx (xx.x%)	xx (xx.x%)	xx (xx.x%)	0.xxx	0.xx	XX.XXX	XX.XXX	XX.XXX

1 Chi-squared test

Table 102: Summary of Vital Signs and Body Weights

Parameter	N	Mean	SD	Med	Max	Min
Vital Sign (units)						
Screening						
Placebo	XX	XX.X	XX.X	XX.X	XX.X	XX.X
Oxytocin	XX	XX.X	XX.X	XX.X	XX.X	XX.X
Week 1						
Placebo	XX	XX.X	XX.X	XX.X	XX.X	XX.X
Oxytocin	XX	XX.X	XX.X	XX.X	XX.X	XX.X
Change from baseline						
Placebo	XX	XX.X	XX.X	XX.X	XX.X	XX.X
Oxytocin	XX	XX.X	XX.X	XX.X	XX.X	XX.X
Weeks 1, 2, 3, 4, 6, 8, 10, 13						

Programmers note: vital signs include pulse rate, systolic blood pressure, and diastolic blood pressure. Body weight (lbs) will also be presented for screening, Weeks 6, 8, 10 and 13.

Table 103: Incidence of Abnormal Findings on Physical Exam in Nasal Mucosa

	Placebo	Oxytocin
	(N=xx)	(N=xx)
Abnomal Nasal Mucosa	nn (xx.x%)	nn (xx.x%)

Table 104: Summary of Other Services Used During Treatment Period

	Placebo	Oxytocin
Services	(N=xx)	(N=xx)
Self Help Meetings		
N	XX	XX
Mean	XX.X	XX.X
SD	XXX.XX	XXX.XX
Median	XX	XX
Min-Max	(xx-xx)	(xx-xx)

	Placebo	Oxytocin
Services	(N=xx)	(N=xx)
Have you visited another health professional to get help reducing drinking?		
N	Xx	XX
Yes n (%)	xx (xx)	xx (xx)

Programmer note: categorize type of professional for those categories reaching 5%

Table 105: Summary of ECG Results

	ASP8062	Placebo
Result	(N=xx)	(N=xx)
Screening		
Normal	nn (xx.x%)	nn (xx.x%)
Abnormal, Not Clinically Significant	nn (xx.x%)	nn (xx.x%)
Abnormal, Clinically Significant	nn (xx.x%)	nn (xx.x%)
End of Study		
Normal	nn (xx.x%)	nn (xx.x%)
Abnormal, Not Clinically Significant	nn (xx.x%)	nn (xx.x%)
Abnormal, Clinically Significant	nn (xx.x%)	nn (xx.x%)

Table 106: Summary of Blood Chemistries

		Placebo				Oxytocin						
Test	N	Mean	SD	Med	Min	Max	N	Mean	SD	Med	Min	Max
Test Name (units)												
Screening												
Week 6												
Change from baseline												
Weeks 8, 10, 13												

Programmers note: table will include creatinine, ALT, AST, total bilirubin, creatinine, sodium, and potassium.

Table 107: Summary of Positive Urine Drug Tests, Pregnancy Test or BAC > 0.000 Any Time During the Study

	Number (% Positive)					
Test	Placebo	Oxytocin				
THC	xx (xx%)	xx (xx%)				
Cocaine	xx (xx%)	xx (xx%)				
Opioids	xx (xx%)	xx (xx%)				
Methamphetamine	xx (xx%)	xx (xx%)				
Amphetamine	xx (xx%)	xx (xx%)				
Benzodiazapines	xx (xx%)	xx (xx%)				
Buprenorphine	xx (xx%)	xx (xx%)				
Methadone	xx (xx%)	xx (xx%)				
Oxycodone	xx (xx%)	xx (xx%)				
MDMA	xx (xx%)	xx (xx%)				
Barbiturates	xx (xx%)	xx (xx%)				
Pregnancy	xx (xx%)	xx (xx%)				
BAC > 0.000	xx (xx%)	xx (xx%)				

Table 108: BPAQ – Each Evaluation During Maintenance Period

			0	xytocin			Placebo						
Study Week	N	Mean	SD	Median	Min	Max	N	Mean	SD	Median	Min	Max	
Physical Aggression													
6	XX	XXX	XXX	XXX	XXX	XXX	XXX	XXX	XXX	XXX	XXX	XXX	
8	XX	XXX	XXX	XXX	XXX	XXX	XXX	XXX	XXX	XXX	XXX	XXX	
10	XX	XXX	XXX	XXX	XXX	XXX	XXX	XXX	XXX	XXX	XXX	XXX	
13	XX	XXX	XXX	XXX	XXX	XXX	XXX	XXX	XXX	XXX	XXX	XXX	
Verbal Aggress	ion												

6	XX	XXX										
8	XX	XXX										
10	XX	XXX										
13	XX	XXX										
Hostility												
6	XX	XXX										
8	XX	XXX										
10	XX	XXX										
13	XX	XXX										
Anger												
6	XX	XXX										
8	XX	XXX										
10	XX	XXX										
13	XX	XXX										

Table 109: BPAQ Physical Aggression Score -- Full Model, Mixed Effects, Entire Maintenance Period

Type III Wald Tests¹

Parameter	Num DF	Den DF	F Value	p-value
ARM	1	XXX	XXX.XX	0.xxx
Week	3	XXX	XXX.XX	0.xxx
Site	9	XXX	XXX.XX	0.xxx
Baseline Total Score	X	XXX	XXX.XX	0.xxx
ARM*Week	3	XXX	xxx.xx	0.xxx

¹Values in Type III table are based upon transformed data {note to specify which transformation}

Least Squares Means

				95%	95% CI			Untran	sformed	Transformed	
Arm	Week	Estimate	SE	Lower CI	Upper CI	Difference	SE	p-value	Cohen's d	p-value	Cohen's d
Oxytocin	6	XX.XX	0.xxx	0.xxx	0.xxx	X.XXX	X.XXX	0.xxx	XX.XXX	0.xxx	XX.XXX
Placebo	6	XX.XX	0.xxx	0.xxx	0.xxx						
Oxytocin	8	XX.XX	0.xxx	0.xxx	0.xxx	X.XXX	X.XXX	0.xxx	XX.XXX	0.xxx	XX.XXX
Placebo	8	XX.XX	0.xxx	0.xxx	0.xxx						
Oxytocin	10	XX.XX	0.xxx	0.xxx	0.xxx	X.XXX	X.XXX	0.xxx	XX.XXX	0.xxx	XX.XXX
Placebo	10	XX.XX	0.xxx	0.xxx	0.xxx						
Oxytocin	13	XX.XX	0.xxx	0.xxx	0.xxx	X.XXX	X.XXX	0.xxx	XX.XXX	0.xxx	XX.XXX
Placebo	13	XX.XX	0.xxx	0.xxx	0.xxx						
Oxytocin	Overall	XX.XX	0.xxx	0.xxx	0.xxx	X.XXX	X.XXX	0.xxx	XX.XXX	0.xxx	XX.XXX
Placebo	Overall	XX.XX	0.xxx	0.xxx	0.xxx						

Table 110: BPAQ Verbal Aggression Score -- Full Model, Mixed Effects, Entire Maintenance Period

Shell is same style as Table 109

Table 111: BPAQ Anger Score -- Full Model, Mixed Effects, Entire Maintenance Period

Shell is same style as Table 109

Table 112: BPAQ Hostility Score -- Full Model, Mixed Effects, Entire Maintenance Period

Shell is same style as Table 109

Table 113: SNAQ – Untransformed, Each Evaluation During Maintenance Period

		Oxytocin						Placebo					
Study Week	N	Mean	SD	Median	Min	Max	N	Mean	SD	Median	Min	Max	
6	XX	XXX	XXX	XXX	XXX	XXX	XXX	XXX	XXX	XXX	XXX	XXX	
8	XX	XXX	XXX	XXX	XXX	XXX	XXX	XXX	XXX	XXX	XXX	XXX	
10	XX	XXX	XXX	XXX	XXX	XXX	XXX	XXX	XXX	XXX	XXX	XXX	
13	XX	XXX	XXX	XXX	XXX	XXX	XXX	XXX	XXX	XXX	XXX	XXX	

Table 114: SNAQ Score ≤ 14 at Each Visit During Treatment

							95% CI	
	Placebo	Oxytocin	Total					
	(N=xx)	(N=xx)	(N=xxx)	p-value ¹	Cohen's h	Odds Ratio	OR Lower CI	OR Upper CI
SNAQ Score ≤ 14								
Week 6	xx (xx.x%)	xx (xx.x%)	xx (xx.x%)	0.xxx	0.xx	XX.XXX	XX.XXX	XX.XXX
Week 8	xx (xx.x%)	xx (xx.x%)	xx (xx.x%)	0.xxx	0.xx	XX.XXX	XX.XXX	XX.XXX
Week 10	xx (xx.x%)	xx (xx.x%)	xx (xx.x%)	0.xxx	0.xx	XX.XXX	XX.XXX	XX.XXX
Week 13	xx (xx.x%)	xx (xx.x%)	xx (xx.x%)	0.xxx	0.xx	XX.XXX	XX.XXX	XX.XXX

1 Chi-squared test

Table 115: SNAQ Total Score -- Full Model, Mixed Effects, Entire Maintenance Period

Shell is same style as Table 109

Table 116: Frequency of Subjects with Suicidal Ideation Any Time During the Study

Number of Subjects Re	Number of Subjects Reporting Suicidal Ideation by C-SSRS (%)										
Placebo Oxytocin p-value											
(N=xx)	(N=xx)										
xx (xx.x%)	xx (xx.x%)	0.xxx									

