#### **Safety Analyses:**

The severity, frequency, and relationship of AEs to investigational product will be presented by Medical Dictionary for Regulatory Activities (MedDRA) System Organ Class (SOC) and Preferred Term (PT) grouping. AE summary data will be presented by dose (all weeks, first two weeks and last 10 weeks). Listings of each individual AE including start date, stop date, severity, relationship, outcome, and duration will be provided. Clinical chemistry, urine drug screen results, pregnancy test results, and BAC results, will be reported as summary statistics. Vital signs will be presented as summary statistics and change from baseline. The proportions of ECG results considered clinically significant will also be provided. In addition, change from baseline (shift tables) will also be presented for clinical chemistry data. The numbers and proportion of subjects who reported CIWA-AR scores ≥ 10 at any time after the start of dosing will be presented. Buss-Perry Aggression scores and SNAQ scores will be compared using repeated measures ANOVA. The numbers and proportions of subjects mild, moderate, severe microsomia or any smell loss (anosmia) compared with screening assessment using the UPSIT will also be presented.

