# 6. Study Interventions

# 6.1. Investigational Products: Oxytocin and Placebo

Investigational products will be manufactured under contract with University of Iowa and will be packaged and distributed in drug kits by Catalent, Inc. Oxytocin and Placebo liquid formulations will be packaged in 20 mL vials with a fill volume of 18 mL with a Nemera P270 pump spray actuator device crimped to the vial. Oxytocin is supplied at a concentration of 70 IU/mL. The pump spray actuator delivers  $100 \, \mu L$  in a single spray (equivalent to 7 IU of oxytocin).

Oxytocin and placebo will be administered once daily (morning) for 2 weeks (Weeks 1 and 2) and then twice daily (morning and evening) for 10 weeks (Weeks 3 through 12). One dose is defined as the intranasal administration of  $100~\mu L$  per each nostril for a total of 5 insufflations alternating between nostrils with a 30 second wait between insufflations for a total dose of 500  $\mu L$  equivalent to 35 IU. Thus, subjects will receive oxytocin 35 IU per day for 2 weeks, then 35 IU twice per day for 10 weeks for a total daily dose of oxytocin 70 IU.

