#### 7.8. Treatment Phase

During Study Weeks 1 through 12 of the treatment phase of the study, subjects will be seen in person at the clinical site 7 times and assessed by telephone 5 times. There is a final clinic visit at Week 13 at the end of the 12-week treatment period.

An alcohol breathalyzer will be administered at each visit, prior to any study assessments, to determine if the subject meets the BAC requirement of a BAC  $\leq$  0.020 before proceeding with assessments. A urine drug test will be performed at each visit. At each of the clinic visits, subjects will meet with one or more study staff members who will systematically assess AEs since the last visit, take vital signs, collect concomitant medication use, administer questionnaires (CIWA-AR and C-SSRS), inquire about other medication use and assess drinking by TLFB. The UPSIT sniff card test and clinical chemistry, pregnancy test for women of child-bearing potential and birth control methods (if female) will be collected in accordance with the schedule in Table 3. An examination of the nasal mucosa will also be performed. In addition, subjects will electronically complete the questionnaires according to the schedule in Table 3. If the subject is returning a used study drug vial, the vial will be weighed and the diary card will be reviewed for compliance.

Brief telephone assessments will occur at Weeks 5, 7, 9, 11, and 12. The final in-clinic assessment will occur during Week 13. This visit should be scheduled after the subject takes the last dose of study drug.

Subjects will view a single module of Take Control at all clinic visits up to and including Week 10 that is expected to have a run-time of 10-15 minutes at clinic visits. The subject will be

instructed to bring the nasal spray vials and drug with them to the next visit so the site staff can perform drug accountability. The subject will also be instructed to contact site staff if they are experiencing any intolerable AEs and are contemplating drug discontinuation.

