#### 7.10. Final Clinic Visit

The final clinic visit occurs during Week 13; at which time the subject has completed taking investigational product. In addition to the assessments previously stated, subjects will have an Exit Interview assessment. The subject will be asked about their impression of whether they were receiving active drug or placebo, if they felt that the medication helped drinking, how they

would describe their experience taking the medication, if they would recommend it to a friend, if they would take it again if they needed further treatment in the future. The subject will be provided with a referral to a treatment program for their alcohol dependence. If a subject withdraws from the study early for any reason, the subject should be asked to return to the clinic for the conduct of all of the final clinic visit assessments.

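### The by-dose AE tables stop at Week 12 with no rule for assigning AEs to a period, so test-detected AEs dated to the Week 13 visit fall in neither dose table and a Day 15 smell-test AE counts under the wrong regimen

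*SAP*

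**What the plan says.** The Safety Analyses paragraph of the protocol synopsis gives the purpose of the split: "AE summary data will be presented by dose (all weeks, first two weeks and last 10 weeks".

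SAP section 12.1.4 carries this out by study week. Table 91 is described as "Same as Table 90 except only the first 2 weeks". The maintenance table is titled "Table 92: Number and Percentage of Subjects with Adverse Events During Weeks 3-12" and described as "Same as Table 90 except only the last 10 weeks". The maximum-severity versions, Tables 96 and 97, use the same cuts; Table 97 reads "Same as Table 95 using only weeks 3-12". No by-dose table covers Week 13 or later.

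On dosing and visits, Protocol 6.1 puts maintenance dosing at "twice daily (morning and evening) for 10 weeks (Weeks 3 through 12". Protocol 7.10 states: "The final clinic visit occurs during Week 13; at which time the subject has completed taking investigational product". Protocol 7.8 adds: "This visit should be scheduled after the subject takes the last dose of study drug". The schedule of assessments places chemistry, UPSIT, vital signs, physical exam and the end-of-study ECG at Week 13. Weeks 11 and 12 are telephone contacts without tests.

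On what counts as an AE, Protocol 10.2.4 makes abnormal laboratory values and rises in blood pressure grade reportable, Protocol 10.34 does the same for UPSIT scores in the reduced-smell bands, and SAP 9.6.8 sends UPSIT outcomes to the AE tables. SAP 9.6.1 and Listing 26 record AE start dates. Neither document says whether an AE enters a period by onset date, by detection date or by the regimen being taken.

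**The concern.** The split exists to describe safety at each dose, but its boundaries are calendar weeks and the tests do not line up with them. At the end, the visit with the greatest cumulative exposure lies one day past the window. At the start, the first post-dose UPSIT nominally falls on the first day of the new regimen and so reflects the regimen just finished. Laboratory changes such as low sodium, and measured loss of smell, are found mainly by these scheduled tests, and a test finding often has no known onset other than the visit date.

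The matter counts most for smell. Apart from a baseline table and a listing, the SAP reports UPSIT only through the AE tables, so Tables 91, 92, 96 and 97 are its only by-dose summary. The cut-off also departs from the SAP's own practice. SAP 9.4.2 includes Week 13 questionnaires among the treatment-period data for continuous secondary endpoints, and the BPAQ and SNAQ tables labelled as maintenance period (Tables 108-113 and 115) include Week 13.

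**Working it through.** **Inputs.** Study weeks and visits from the schedule of assessments (Protocol Table 3, SAP Table 1); windows from SAP 12.1.4; once-daily dosing on Days 1-14 from the diary card in Protocol Appendix A. Nominal visit day = 7 × (week − 1) + 1.

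**The plan's own window.** Weeks 3-12 is 12 − 3 + 1 = 10 weeks, Days 15 to 84, or 70 days. This agrees with the stated 10 weeks.

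**Placing each scheduled post-dose test.** Assumption: a test-detected AE is dated to its visit, since the SAP gives no rule. Week 2 = Day 8, Week 3 = Day 15, Week 4 = Day 22, Week 6 = Day 36, Week 8 = Day 50, Week 10 = Day 64, Week 13 = Day 85.

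| Test | Visit weeks | In Weeks 1-2 | In Weeks 3-12 | In neither |
|---|---|---|---|---|
| UPSIT | 3, 6, 8, 10, 13 | 0 | 4 | 1 |
| Chemistry | 6, 8, 10, 13 | 0 | 3 | 1 |
| ECG | 13 | 0 | 0 | 1 |
| Nasal exam, vital signs | 2, 3, 4, 6, 8, 10, 13 | 1 | 5 | 1 |

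**The end gap.** From the Week 10 visit (Day 64) to the last dosing day (Day 84) is 84 − 64 + 1 = 21 days, and 21/70 = 30% of maintenance dosing. Week 13 is the only scheduled clinic testing for that stretch.

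**Exposure at the Week 3 visit.** Count doses before the visit day: 14 once-daily doses, plus 2 × (visit day − 15) doses on the twice-daily schedule.
- Day 15: 14/(14 + 0) = 100% once-daily.
- Day 18: 14/(14 + 6) = 70%.
- Day 21: 14/(14 + 12) = 54%.

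**Possible share of findings, on stated assumptions only.** The documents give no onset rates.
- Persistent chemistry findings with uniform onset over the 84 dosing days, dated to the detecting visit: 21/84 = 25% are first seen at Week 13. Among onsets during twice-daily dosing the figure is 21/70 = 30%.
- Transient findings with a constant chance h of detection at each of four chemistry visits: the share of first detections at Week 13 is (1 − h)³h / [1 − (1 − h)⁴], which is 24%, 23% and 21% for h = 0.02, 0.05 and 0.10.
- Persistent UPSIT findings with uniform onset: 14/84 = 17% are first seen at a Day 15 Week 3 visit and counted under twice-daily dosing.

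**After assigning by the regimen taken before the test** (nominal days): UPSIT becomes 1 once-daily and 4 twice-daily; chemistry 0 and 4; ECG 0 and 1; nasal exam and vital signs 2 and 5. None is unassigned.

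**The case against.** The strongest reply is that the SAP never assigns AEs by detection visit. Each AE has a recorded start date, staff ask about the interval since the last contact, and the Week 11 and 12 calls cover AEs. A symptom first mentioned at Week 13 but starting by Day 84 can enter Table 92. This stands, and it limits the point to test-detected findings dated to the visit.

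A reader might infer that Table 91 can never hold a smell finding and that every post-dose ECG finding is excluded. The documents do not support that. End-of-study tests are also done at early discontinuation when the subject agrees to a final visit, and extra safety visits are allowed, so such findings can fall inside either window. The counts above describe scheduled visits for subjects who complete.

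A reader might also expect the two dose tables to add up to Table 90. They would not under any cut-off, because they count subjects, and one subject can have the same event in both periods.

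Finally, no Week 13 finding disappears from the report. Tables 89, 90, 93-95 and 98-100 have no week limit, Tables 102-106 include vital signs, nasal findings, ECG and chemistry through the end of study, and the cut-off is the same in both arms. This also stands. What it does not answer is that the protocol asked for a summary by dose, and the maintenance table leaves out the tests that close the maintenance period.

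**Conclusion.** The point holds for the by-dose split only. Tables 92 and 97 have a stated cut-off at Week 12, and neither document has an assignment rule. Test-detected AEs first found at the scheduled Week 13 visit and dated to it therefore enter neither dose table, although that visit is the only clinic testing for the last 30% of maintenance days. A UPSIT AE at a nominal Day 15 visit is counted under twice-daily dosing after once-daily exposure alone; with a later Week 3 visit the exposure is mixed.

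The 30% is a share of dosing days. The proportion of AEs affected is not known: the 17% and 21% to 30% figures need visit dating, nominal visit days, no dropout and either uniform persistent onset or constant detection per visit. The all-weeks comparison between arms is complete and is not in question.

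**What to change.** In SAP 12.1.4, with a matching rule in 9.6.1:
- Extend the maintenance period in Tables 92 and 97 through the Week 13/EOS visit, as the SAP's other maintenance-period tables already do.
- Assign each AE to one period by the regimen taken before its onset date, or before the detecting test when onset is unknown. A Week 3 finding goes to the once-daily period only if no twice-daily dosing preceded it.
- Show AEs that start after the Week 13/EOS visit in a separate follow-up column.
- State how subjects who never start twice-daily dosing are shown. Protocol 6.7 provides that subjects whose dose is reduced in the first two weeks do not move to the maintenance dose.
- Do not require the columns to sum to Table 90.

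The cost is a small amount of extra derivation and shell work before unblinding. AE start dates and dated diary doses are already collected, so no new data are needed.
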